2.4 Clinical Hypotheses

The primary clinical hypothesis is that long-term exposure of evolocumab will be safe and well tolerated in subjects with clinically evident atherosclerotic CVD.

3. EXPERIMENTAL PLAN

3.1 Study Design

This is a multicenter, open-label extension study designed to assess the long-term safety of evolocumab in subjects who completed the FOURIER study, a randomized placebo-controlled study of evolocumab in subjects with clinically evident atherosclerotic CVD on stable effective statin therapy. Eligible subjects at sites participating in FOURIER OLE who have signed the FOURIER OLE informed consent may be enrolled at the completion of FOURIER. Enrollment of eligible subjects may be limited at the site level to maintain a 1:1 ratio between the following subject populations:

- subjects with \geq 2 years of study exposure in FOURIER and
- subjects who have less than 2 years of study exposure in FOURIER and did not participate in EBBINGHAUS

In this study, laboratory assessments will be performed at week 12 and thereafter approximately every 24 weeks from day 1 (see [Section 7.2](#)); the corresponding blood samples will be processed using a central laboratory. To preserve the integrity of FOURIER blinding, no local lipid assessments may be performed until either FOURIER is unblinded or at least 12 weeks after a subject's last administration of FOURIER investigational product (evolocumab or placebo), whichever is first. Upon enrollment in this study (FOURIER OLE), subjects will receive evolocumab 140 mg every 2 weeks (Q2W) or 420 mg monthly (QM), according to their preference. Frequency and corresponding dose of administration can be changed at any scheduled time point where evolocumab is supplied to the subject, provided the appropriate supply is available. It is recommended that subjects continue the same background LLT, including statin, as taken during FOURIER. This study will continue for 260 weeks (approximately 5 years). Subjects ending administration of evolocumab should continue study assessments until the end of study (EOS).

All subjects will be followed and complete procedures/assessments from enrollment through the date of study termination unless the subject has withdrawn consent, irrespective of whether the subject is continuing to receive treatment. All deaths and cardiovascular events of interest (MI, stroke, coronary revascularization, hospitalization for unstable angina, hospitalization for heart failure, and transient ischemic attack [TIA]) will be reviewed by an independent external Clinical Events Committee (CEC), using standardized definitions.

The overall study design is described by a [study schema](#) at the end of the protocol synopsis section.

The study endpoints are defined in [Section 10.1.1](#).

3.2 Number of Sites

Approximately 250 centers will participate in this study in North America and Eastern Europe. Sites that do not enroll subjects within 3 to 6 months of site initiation may be closed.

3.3 Number of Subjects

Participants in this clinical investigation shall be referred to as "subjects." Approximately 5000 subjects will be enrolled, including approximately 2000 subjects with ≥ 2 years of study exposure in FOURIER.

3.4 Replacement of Subjects

Subjects who are withdrawn or removed from treatment or the study will not be replaced.

3.5 Estimated Study Duration

3.5.1 Study Duration for Subjects

The study will continue for 260 weeks (approximately 5 years).

3.5.2 End of Study

Primary Completion: The primary completion date is defined as the date when the last subject is assessed or receives an intervention for the final collection of data for the primary endpoint(s), whether the study concluded as planned in the protocol or was terminated early.

The primary completion date is the date when the last subject has completed the assessments for EOS/safety follow-up.

If the study concludes prior to the primary completion date originally planned in the protocol (ie, early termination of the study), then the primary completion will be the date when the last subject is assessed or receives an intervention for evaluation in the study (ie, last subject last visit).

End of Study: The end of study date is defined as the date when the last subject is assessed or receives an intervention for evaluation in the study (ie, last subject last visit), following any additional parts in the study (eg, safety follow-up), as applicable.

4. SUBJECT ELIGIBILITY

4.1 Inclusion and Exclusion Criteria

4.1.1 Inclusion Criteria

- 101 Subject has provided informed consent before initiation of any study-specific activities/procedures.
- 102 Subject has completed FOURIER (Study 20110118) while still receiving assigned investigational product.

4.1.2 Exclusion Criteria

- 201 Investigational product was permanently discontinued during FOURIER for any reason, including an adverse event or serious adverse event.
- 202 Subject is currently receiving treatment in another investigational device or drug study, or ended treatment on another investigational device or drug study(ies) within less than 4 weeks. Other investigational procedures while participating in this study are excluded.
- 203 Subject is not likely to be available to complete protocol-required study visits or procedures and/or to comply with required study procedures to the best of the subject's and investigator's knowledge.

204 Subject has a history or evidence of any other clinically significant disorder, condition, or disease that, in the opinion of the investigator or Amgen physician, if consulted, would pose a risk to subject safety or interfere with the study evaluation, procedures, or completion.

205 Subject has a known sensitivity to any of the active substances or excipients (eg, sodium acetate) to be administered during dosing.

206 Female subject is pregnant or breastfeeding or is planning to become pregnant or planning to breastfeed during treatment with evolocumab and within 15 weeks after the end of treatment with evolocumab.

207 Female subjects of childbearing potential who are not willing to use an acceptable method(s) of effective birth control during treatment with evolocumab and for an additional 15 weeks after the end of treatment with evolocumab are excluded.

Female subjects of non-childbearing potential are not required to use contraception during the study and include those who have had a hysterectomy, bilateral salpingectomy, bilateral oophorectomy, or who are postmenopausal. Postmenopausal is defined as 12 months of spontaneous and continuous amenorrhea in a woman \geq 55 years old; or age $<$ 55 years but no spontaneous menses for at least 2 years; or age $<$ 55 years and spontaneous menses within the past 1 year, but currently amenorrheic (eg, spontaneous or secondary to hysterectomy), and with postmenopausal gonadotropin levels (luteinizing hormone and follicle-stimulating hormone [FSH] levels $>$ 40 IU/L), postmenopausal estradiol levels ($<$ 5 ng/dL), or according to the definition of postmenopausal range for the laboratory involved.

Acceptable methods of effective birth control include true sexual abstinence (when this is in line with the preferred and usual lifestyle of the subject; periodic abstinence [eg, calendar, ovulation, symptothermal, postovulation methods], declaration of abstinence for the duration of a trial, and withdrawal are not acceptable methods of contraception), bilateral tubal ligation/occlusion, vasectomized partner (provided the vasectomized male has received medical assessment of surgical success), use of hormonal birth control methods (oral, intravaginal, transdermal, injectable, or implantable), intrauterine devices, intrauterine hormonal releasing system, or 2 barrier methods (each partner must use one barrier method) and the female partner must use spermicide in addition to a barrier method (men must use a condom; women must choose either a diaphragm, cervical cap, or contraceptive sponge [a female condom is not an option because of the risk of tearing when both partners use a condom]). If spermicide is not commercially available in the country or region, the 2-barrier method without spermicide is acceptable. Note: Additional medications given during treatment with evolocumab may alter the contraceptive requirements. These additional medications may require the use of highly effective methods of contraception, an increase in the number of contraceptive methods, a change in type of contraceptive methods, and/or an increase in the length of time that contraception is to be utilized or length of time that breastfeeding is to be avoided. The investigator is to discuss these contraceptive changes with the study subject.

5. SUBJECT ENROLLMENT

Before subjects begin participation in any study-specific activities/procedures, Amgen requires a copy of the site's written institutional review board/independent ethics committee (IRB/IEC) approval of the protocol, informed consent form (ICF), and all other subject information and/or recruitment material, if applicable (see [Section 11.2](#)). All subjects must personally sign and date the IRB/IEC- and Amgen-approved ICF before commencement of study-specific activities/procedures.

A subject is considered enrolled when the investigator decides that the subject has met all eligibility criteria. The investigator is to document this decision and date, in the subject's medical record and on the enrollment electronic case report form (eCRF).

Each subject who signs the IRB/IEC-approved ICF is to be assigned the same subject identification number for this OLE study as the parent study (FOURIER) before any study procedures are performed. This number will be used to identify the subject throughout the clinical study and must be used on all study documentation related to that subject.

The subject identification number must remain constant throughout the entire clinical study; it must not be changed.

5.1 Treatment Assignment

All subjects will receive open-label evolocumab.

6. TREATMENT PROCEDURES

6.1 Classification of Products and/or Medical Devices

The Amgen investigational medicinal product used in this study is evolocumab (AMG 145). In several countries, investigational product is referred to as investigational medicinal product. In this document, investigational medicinal product will be referred to as investigational product (evolocumab).

The non-Amgen non-investigational products used in this study include background LLTs, including a statin.

Evolocumab will be provided by prefilled autoinjector/pen (AI/Pen) or **personal injector (PI)**.

Note: Ancillary devices (ie, medical devices not under study) are described in [Section 6.6](#).

The Investigational Product Instruction Manual (IPIM), a document external to this protocol, contains detailed information regarding the storage, preparation, destruction, and administration of evolocumab and information about background LLT and the investigational medical devices used in this study.

6.2 Investigational Product - Evolocumab

Evolocumab (AMG 145) will be manufactured and packaged by Amgen Inc. and distributed using Amgen clinical investigational product distribution procedures.

Evolocumab will be provided as follows:

- an AI/Pen, as a single-use, disposable, handheld mechanical (spring-based) device for fixed dose, subcutaneous (SC) injection of a 1.0-mL deliverable volume of 140 mg/mL evolocumab
- a PI, as a single-use, disposable, on-body electromechanical injection device that is copackaged with a prefilled Crystal Zenith cartridge containing a 3.5-mL deliverable volume of 120 mg/mL evolocumab

Evolocumab should be stored refrigerated and protected from light according to the storage and expiration information provided on the label (where required). Evolocumab should be handled per the instructions provided in the IPIM and the instructions for use (IFU) for the prefilled AI/Pen or PI.

The prefilled AI/Pen or PI should be inspected for investigational product quality, expiry, and damage before using. Damaged, expired, or degraded product should not be used and any issues with the prefilled AI/Pen or PI should be reported to Amgen. Further details are provided in the IPIM and IFU.

Evolocumab will be supplied to the subject at the site. The method of resupply will be determined based on local regulations as well as available infrastructure. The investigator may be required to record the box number of evolocumab (prefilled AI/Pen or PI) on the subject's Drug Administration eCRF. Subjects should return used evolocumab for reconciliation by the site.

6.2.1 Dosage, Administration, and Schedule

Evolocumab will be administered SC for approximately 260 weeks in accordance with the instructions in the IPIM and IFU. The subject (or designee, if not a qualified healthcare professional) must have demonstrated competency at administration of SC injections before self-administration is permitted. The first self-administered dose by the subject (or designee, if not a healthcare professional) may be administered at the site under the supervision of a healthcare provider at day 1. In this study, evolocumab will

Approved

be administered by self-administration by the subject, designee, or a qualified healthcare professional in a non-investigator site setting (eg, at home). In exceptional circumstances, SC administration of evolocumab by a qualified healthcare professional in a clinic setting will also be allowed.

If evolocumab is administered at the study site, the date and completion time of administration, the body location of the injection, whether the injection was fully or partially administered, and box number are to be recorded on each subject's eCRF.

When evolocumab is administered at a non-investigator site location, at a minimum, the dates the devices were dispensed, and the used devices returned, the number of devices returned, box numbers, and for each device whether it was returned fully or partially used are to be recorded on each subject's eCRF.

It is suggested that the evolocumab administration is done by the subject under site staff supervision at each of the regular study visits to ensure continued proper use of the injection device. Evolocumab administration at a scheduled visit, if applicable, is to be performed after completion of the blood draws and vital signs.

Details of preparing evolocumab, the injection procedures, and device disposal are included in the IPIM and IFU provided by Amgen before the start of the study.

Subjects will have the opportunity to switch between evolocumab Q2W and QM at any scheduled time point where evolocumab is supplied to the subject, provided the appropriate supply is available. The first self-administration after switching the dose and frequency (140 mg Q2W to 420 mg QM or vice versa) should be done at a regularly scheduled visit under the supervision of the investigator or qualified study center staff. Subjects who choose QM treatment will initiate treatment using the **PI**, provided the appropriate supply is available. If the **PI** is not available, then the AI/Pen may be used.

If a subject dose of evolocumab is missed, administration should occur as soon as possible if there are more than 7 days until the next scheduled dose. If there are less than 7 days before the next scheduled dose, the missed dose should be omitted, and the next dose should be administered according to the original schedule.

Evolocumab will be administered either at 140 mg in 1.0 mL (1 administration by prefilled AI/Pen) Q2W or at 420 mg in 3.0 mL or 3.5 mL (3 administrations by prefilled AI/Pen or 1 administration by **PI**, respectively) QM. The 3 injections for the QM administration, if applicable, can be administered into different injection sites. The SC injections should be administered in a consecutive fashion with all injections completed within 30 minutes.

6.2.2 Dosage Adjustments, Delays, Rules for Withholding or Restarting, Permanent Discontinuation

No dose adjustments of evolocumab will be allowed in this study.

If, in the opinion of the investigator, a subject is unable to tolerate evolocumab, that subject will discontinue evolocumab but should continue to return for all other study procedures and measurements until the EOS.

The decision to rechallenge the subject after therapy changes should be discussed and agreed unanimously by the subject, investigator, and Amgen. If signs or symptoms recur with rechallenge of evolocumab, then evolocumab should be permanently discontinued.

Stopping and rechallenge rules due to hepatotoxicity are provided in [Section 6.4](#).

6.3 Non-Amgen Non-investigational Products - Background Lipid-lowering Therapy

Non-Amgen non-investigational products, including background LLT, will also be used in this study. Additional details regarding the products are provided in the IPIM.

6.3.1 Dosage, Administration, and Schedule

It is recommended that subjects continue the same background LLT, including statin, as taken while in FOURIER (Study 20110118). All background LLT adjustments must be clearly documented and recorded on the appropriate eCRF page and in the source documents. The dose, start date/time, stop date/time, and frequency of non-Amgen non-investigational product are to be recorded on each subject's eCRF. Background LLT will not be provided by Amgen unless required by local regulations.

Recommendations for background LLT are provided in [Appendix D](#).

All other drugs that are allowed per protocol and that are prescribed for the subject must be commercially available and used at dosages approved by local regulatory authorities. These therapies will not be provided or reimbursed by Amgen (except if required by local regulation).

Subjects should consult the investigator if they miss a dose of background statin.

6.3.2 Dosage Adjustments, Delays, Rules for Withholding or Restarting, Permanent Discontinuation

The investigator should consult the local product label for information on dose adjustments, delays, withholding, restarting, or permanent discontinuation of background LLT, including statins.

If a subject has elevated ad hoc laboratory values ([Section 6.4](#)) and is receiving background LLT, including statins, that may result in such elevations (eg, ezetimibe, fenofibrate, or niacin), the additional therapies should be evaluated for a potential role in the elevated laboratory values and considered for discontinuation. If a subject has elevations in triglycerides > 500 mg/dL (5.65 mmol/L) and is concomitantly receiving a bile acid binding resin, the bile acid binding resin should be evaluated for discontinuation.

The decision to rechallenge the subject after therapy changes should be discussed and agreed unanimously by the subject, investigator, and Amgen. If signs or symptoms recur with rechallenge of statin background therapy, the statin may be substituted by another statin in consultation with the Amgen medical monitor, if possible, or the statin therapy may be discontinued. If signs or symptoms recur with rechallenge of other applicable lipid background therapy, this therapy may be discontinued.

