For subjects who do not meet the criteria for permanent discontinuation of evolocumab outlined above and have no underlying liver disease, the following rules are recommended for withholding of evolocumab, statins, and other applicable lipid background therapies:

- elevation of either AST or ALT according to the following:
 - $> 8 \times \text{ULN}$ at any time
 - $> 5 \times \text{ULN}$ but $< 8 \times \text{ULN}$ for ≥ 2 weeks
 - $> 5 \times \text{ULN}$ but $< 8 \times \text{ULN}$ and unable to adhere to enhanced monitoring schedule
 - $> 3 \times \text{ULN}$ with clinical signs or symptoms that are consistent with hepatitis (eg, right upper quadrant pain/tenderness, fever, nausea, vomiting, jaundice)
- OR TBL $> 3 \times \text{ULN}$ at any time
- OR ALP $> 8 \times \text{ULN}$ at any time

Evolocumab, statins, and other applicable lipid background therapies should be withheld pending investigation into alternative causes of DILI. If evolocumab is withheld, the subject is to be followed according to recommendations in [Appendix A](#) for possible DILI. Rechallenge may be considered if an alternative cause for impaired liver tests (ALT, AST, ALP) and/or elevated TBL is discovered and the laboratory abnormalities resolve to normal or baseline ([Section 6.4.3](#)).

6.4.3 Criteria for Rechallenge of Amgen Investigational Product and Other Protocol-required Therapies After Potential Hepatotoxicity

The decision to rechallenge the subject should be discussed and agreed upon unanimously by the subject, investigator, and Amgen.

If signs or symptoms recur with rechallenge, then evolocumab, statins, and other applicable lipid background therapies should be permanently discontinued. Subjects who clearly meet the criteria for permanent discontinuation (as described in [Section 6.4.1](#)) should never be rechallenged.

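### Protocol 6.3.2 and 6.4.3 conflict on background lipid therapy when hepatic signs or symptoms recur on rechallenge, and 6.4.3 does not name the product whose rechallenge triggers the stop

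*Protocol*

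**What the plan says.** Three sections of the protocol bear on this point.

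**Section 6.3.2** covers background lipid-lowering therapy only. Its trigger refers to the hepatotoxicity section: "If a subject has elevated ad hoc laboratory values ([Section 6.4](#)) and is receiving background LLT, including statins". The first response is that "the additional therapies should be evaluated for a potential role in the elevated laboratory values and considered for discontinuation". Rechallenge needs the unanimous agreement of subject, investigator and sponsor. If the problem returns on the statin, "If signs or symptoms recur with rechallenge of statin background therapy, the statin may be substituted by another statin", in consultation with the sponsor's medical monitor where possible, "or the statin therapy may be discontinued". For the rest, "If signs or symptoms recur with rechallenge of other applicable lipid background therapy, this therapy may be discontinued".

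**Section 6.4** covers ad hoc hepatic elevations; hepatic tests are not scheduled in this study. Section 6.4.2 sets thresholds in multiples of the upper limit of normal, and above them "Evolocumab, statins, and other applicable lipid background therapies should be withheld pending investigation into alternative causes of DILI". Rechallenge may be considered once another cause is found and the values resolve. Section 6.4.3 asks for the same unanimous agreement and then says: "If signs or symptoms recur with rechallenge, then evolocumab, statins, and other applicable lipid background therapies should be permanently discontinued".

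**Section 6.2.2** covers evolocumab: "If signs or symptoms recur with rechallenge of evolocumab, then evolocumab should be permanently discontinued". It closes by referring the reader to Section 6.4 for hepatotoxicity.

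**The concern.** A subject who has a Section 6.4 elevation, is rechallenged and has a recurrence falls under both 6.3.2 and 6.4.3. One section leaves room to change the statin and keep other lipid therapy; the other has all of it stopped for good. Two sites could handle the same event differently, and each could point to protocol text.

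The first stake is patient safety: a stopping rule should have one reading. The second is the record. SAP 9.6.5 reports how many subjects change their lipid-regulating medication, and a substitution and a permanent stop are different entries. Where the status of evolocumab is in doubt, the tabulation of adverse events that lead to stopping evolocumab (Protocol 10.4.2, SAP 9.5.1) could also be touched. Protocol 8.3.1 lists protocol-specified criteria as a ground for removal from treatment and refers to 6.2.2 for them, which is a further reason for the rule to be unambiguous.

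**Working it through.** No figure is involved, so the check is a comparison of the sections, element by element.

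| Element | 6.3.2 | 6.4.2 / 6.4.3 | 6.2.2 | Result |
|---|---|---|---|---|
| First response to the elevation | Evaluate background therapy and consider stopping it; no threshold | Withhold all lipid therapy and evolocumab above stated thresholds | Refers to 6.4 | Different strength and scope; both can be followed |
| Statin after recurrence | May be replaced or stopped | Should be stopped permanently | Not covered | Conflict |
| Other lipid therapy after recurrence | May be stopped | Should be stopped permanently | Not covered | Conflict in force |
| Evolocumab, recurrence on evolocumab | Not covered | Should be stopped permanently | Should be stopped permanently | Agree |
| Evolocumab, recurrence on statin alone | Not covered | Stopped permanently if read literally; product not named | Own sentence not triggered; refers to 6.4 | Unclear |

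**Do the sections reach the same subjects?** Yes. Section 6.3.2 cites 6.4 in its trigger. Apart from its deference to local labels, the only other trigger it names is triglycerides above 500 mg/dL, which concerns bile acid binding resin alone. The sentence on statin rechallenge therefore most naturally applies to the Section 6.4 elevations.

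**Is there an action that one section allows and the other rules out?** Yes. Moving to another statin is open under 6.3.2 and closed under 6.4.3. Continuing other lipid therapy is likewise open under the first and closed under the second.

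**Does any sentence set the order of precedence?** No. Section 6.2.2 hands hepatotoxicity over to 6.4. Section 6.3.2 uses 6.4 only to describe the laboratory values and then gives its own rule for recurrence.

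**How many subjects?** To be affected, a subject must have an ad hoc test, meet a 6.4.2 criterion, have another cause identified, have the values resolve, be rechallenged by unanimous agreement, and then have a recurrence. Subjects who meet the 6.4.1 criteria drop out, since 6.4.3 bars their rechallenge. The documents give a rate for none of these steps.

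**The case against.** The strongest defence is that 6.4 is the specific rule for hepatotoxicity and 6.3.2 the general rule for background therapy, so the specific one governs. That reading is reasonable, but the protocol does not state it, and the cross-reference inside 6.3.2 brings hepatic elevations into the general rule.

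A second defence is that a site that stops everything complies with both sections, because 6.3.2 also allows the statin and other lipid therapy to be stopped. This is correct. It means the conflict lies between a permission and a directive, and not between two commands. The permission to substitute still contradicts the directive.

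Third, sponsor agreement is needed before any rechallenge, so unnoticed divergence is less likely. This stands as a partial safeguard. Neither section requires that agreement for the action after recurrence, and the consultation on substitution applies only where possible.

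Stronger readings are tempting and are not supported:

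- A reader might infer that the sections give opposite instructions for the initial elevation. They do not: a site can withhold under 6.4.2 while it evaluates the background drugs under 6.3.2, and the 6.4.2 thresholds are introduced as recommendations for subjects without underlying liver disease.
- A reader might infer that 6.3.2 lets evolocumab continue after a recurrence. It is silent on evolocumab because it covers background therapy only, and 6.2.2 sends the reader to 6.4.
- A reader might picture a subject whose whole therapy is withheld, who restarts the statin alone, has a recurrence and carries on with evolocumab. In that case evolocumab is still withheld, so nothing carries on. What the text leaves open is whether the withholding has become permanent.

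**Conclusion.** The point holds in two parts. First, 6.3.2 and 6.4.3 conflict on the statin and on other lipid therapy when hepatic signs or symptoms recur on rechallenge, and no precedence is stated. Second, 6.4.3 does not name the product whose rechallenge triggers the stop, so the status of evolocumab is unclear when only the statin is rechallenged. Where evolocumab itself is rechallenged, 6.2.2 and 6.4.3 agree.

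The number of subjects affected is likely small and cannot be derived from the documents. A reader might assume a rate of meeting a withholding criterion, apply it to the planned 5000 subjects, and read the result as a shift in the incidence of evolocumab withdrawal. That does not follow: most steps come after withholding, only recurrence brings the conflict into play, and 6.3.2 gives no instruction on evolocumab. Sample size and the planned analyses are unaffected. The case rests on the need for one clear stopping rule and not on bias in an endpoint. It assumes that the reference to Section 6.4 in 6.3.2 means the elevations described there. No view is taken on which clinical rule is right.

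**What to change.** Reconcile Protocol 6.2.2, 6.3.2 and 6.4.3:

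- State which section governs hepatic elevations that meet the Section 6.4 criteria, including what happens on recurrence.
- State in 6.4.3 which rechallenged product triggers discontinuation of which therapies, and bring 6.2.2 into line.
- Leave the choice of rule to the sponsor's medical team, and issue the reconciled text to sites.

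The cost is a protocol clarification and a site letter. No new procedures, visits or data are needed.
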